4.3.4. E-RS: COPD total score Responders

4.3.4.1. Definition of Endpoint

The Evaluating Respiratory Symptoms in COPD (E-RS: COPD) consists of 11 items from the 14 item EXACT instrument (completed each evening using an eDiary). E-RS: COPD is intended to capture information related to the respiratory symptoms of COPD, i.e., breathlessness, cough, sputum production, chest congestion, and chest tightness. The E-RS: COPD has a scoring range of 0-40, higher scores indicate more severe symptoms. Three subscales of the E-RS: COPD are used to describe different symptoms (breathlessness, cough and sputum, and chest symptoms).

Daily data will be slotted to baseline and 4-week periods relative to the first dose of IP as defined in Section 6.2.5.4.

The variable of interest is the proportion of E-RS: COPD responders at Week 52, using data from the 4-week period prior to Week 52 (Weeks 49-52). A participant is considered a responder if they have a 2-point or more improvement (reduction) in their average E-RS: COPD total score during a 4-week period compared to baseline (*E-RS™: COPD User Manual, 2016*). Participants who withdrew from study prior to the start of the Weeks 49-52 time-period will be included in the analysis as a non-responder.

Participants who experienced an intercurrent event of IP discontinuation or interruption of 2 or more consecutive doses of IP associated with the COVID-19 pandemic prior to Weeks 49-52 will be considered as having missing data from the time of the intercurrent event. Missing data will be imputed based on the average 4-weekly scores as described in Section 4.3.2.1.

The summary measure of treatment effect will be the odds ratio which represents the relative odds of a participant being a responder at Weeks 49-52 in the mepolizumab arm compared with placebo.

4.3.4.2. Main Analytical Approach

Descriptive statistics and summaries of responders will be presented as detailed in Section 4.3.2.2. with the exception of the responder summary for the Extended Treatment Population. E-RS: COPD total score responders will be analyzed as described in Section 4.3.2.2.

4.3.5. Annualized Rate of Exacerbations Requiring ED visit and/or hospitalization

4.3.5.1. Definition of Endpoint

Frequency of exacerbations requiring ED visit and/or hospitalization over the study treatment period (up to 104 weeks) represented by an annualized rate, these exacerbations are relatively infrequent. Details regarding the estimand strategy for this endpoint are as described in Section [4.2.1](#).

4.3.5.2. Main Analytical Approach

The annualized rate of exacerbations requiring ED visit and/or hospitalization will be analyzed as described in Section [4.2.2](#).

4.4. Other Efficacy Analyses

The population, treatment condition and handling of intercurrent events as described for the primary estimand (Section [4.2.1](#)) apply to all efficacy analyses unless otherwise specified.

4.4.1. Time to first exacerbation (ED/Hospitalization, Severe)

4.4.1.1. Definition of Endpoint

Time to first exacerbation requiring ED and/or hospitalization and time to first severe exacerbation will be determined as detailed in Section [4.3.1.1](#).

4.4.1.2. Main Analytical Approach

The approach to analysis will be as described in Section [4.3.1.2](#).

4.4.2. Annualized Rate of Exacerbations (Severe, Moderate/Severe By Type of Treatment Required)

4.4.2.1. Definition of Endpoint

Frequency of severe exacerbations and frequency of moderate/severe exacerbations by type of treatment required (corticosteroids alone, antibiotics alone or corticosteroids and antibiotics) over the study treatment period (up to 104 weeks) represented by an annualized rate as detailed in Section [4.2.1](#).

4.4.2.2. Main Analytical Approach

The approach to analysis will be as described in Section [4.2.2](#).

4.4.3. Daily eDiary data (Percentage of rescue medication free days, Percentage of nights with no awakenings, Mean number of occasions of rescue medication use/day)

4.4.3.1. Definition of Endpoint

Daily data collected via an eDiary will be slotted to baseline and 4-week periods relative to the first dose of IP as defined in Section 6.2.5.4.

The percentage of rescue medication free days will be calculated at baseline and for each 4-week period as:

$$(100 \times [\text{No. rescue medication free days} / \text{No. days with non-missing data}]).$$

The percentage of nights with no awakenings due to COPD symptoms will be calculated at baseline and for each 4-week period as:

$$(100 \times [\text{No. nights with no awakenings} / \text{No. days with non-missing data}]).$$

The mean number of occasions of rescue medication use per day will be calculated at baseline and for each 4-week period as:

$$(\text{Total occasions of rescue medication use} / \text{No. days with non-missing data}).$$

The summary measure of treatment effect for each endpoint will be the difference between mepolizumab and placebo in mean change from baseline at Weeks 49-52.

4.4.3.2. Main Analytical Approach

Statistical Methodology Specification

Endpoint / Variables									
Percentage of rescue medication free days									
Percentage of nights with no awakenings due to COPD symptoms									
Mean number of occasions of rescue medication use per day									
Model Specification									

 This endpoint will be analyzed using a mixed model repeated measures (MMRM) analysis including data up to Weeks 49-52 and the following terms: 
 
 Fixed Categorical:	Treatment group, smoking status, geographic region, Time period	
 
 Fixed Continuous:	Baseline value	
 
 Repeated:	Time period	
 
 Interaction Terms:	Time period by baseline, Time period by treatment group.	
 
 Participants with missing covariate information will be excluded from the analysis 
An unstructured covariance structure for the R matrix will be used by specifying 'type=UN' on the REPEATED line. In the event that this model fails to converge, alternative correlation structures may be considered.
		Fixed Categorical:	Treatment group, smoking status, geographic region, Time period	Fixed Continuous:	Baseline value	Repeated:	Time period	Interaction Terms:	Time period by baseline, Time period by treatment group.
Fixed Categorical:	Treatment group, smoking status, geographic region, Time period								
Fixed Continuous:	Baseline value								
Repeated:	Time period								
Interaction Terms:	Time period by baseline, Time period by treatment group.								

Model Checking & Diagnostics

 The Kenward-Roger method for approximating the denominator degrees of freedom and correcting for bias in the estimated variance-covariance of the fixed effects will be used.
Model Results Presentation

 The estimated means for each treatment group will be calculated from the model using the observed marginal distributions of the sample covariates (OM option in LSMEANS statement). Model-estimates of the absolute and change from baseline values will be presented by treatment group. Estimated treatment differences (Mepolizumab-Placebo) with corresponding 95% CIs and p-values will also be presented.

4.4.4. Change from baseline (Pre-bronchodilator FEV₁, FVC, CAT Score, SGRQ Total Score, E-RS: COPD Total Score)

4.4.4.1. Definition of Endpoint

Change from baseline pre-bronchodilator FEV₁ at Week 52

Change from baseline pre-bronchodilator FVC at Week 52

Change from baseline CAT score at Weeks 24 and 52

Change from baseline SGRQ Total score at Weeks 24 and 52

Change from baseline ERS: COPD Total score at Weeks 21-24 and Weeks 49-52

For change from baseline CAT, SGRQ and E-RS: COPD: Participants who experienced an intercurrent event of IP discontinuation or interruption of 2 or more consecutive doses of IP associated with the COVID-19 pandemic will be considered as having missing data from the time of the event. Missing data will be imputed as described in Section [4.3.2.1](#).

The summary measure of treatment effect for each endpoint will be the difference between mepolizumab and placebo in mean change from baseline at the respective timepoints.

4.4.4.2. Main Analytical Approach

Statistical Methodology Specification

Endpoint / Variables									

Change from baseline pre-bronchodilator FEV₁ at Week 52 Change from baseline pre-bronchodilator FVC at Week 52 Change from baseline CAT score at Week 24 and 52 Change from baseline SGRQ total score at Week 24 and 52 Change from baseline E-RS: COPD score at Weeks 21-24 and Weeks 49-52
									
Model Specification									

 Endpoints will be analyzed using a mixed model repeated measures (MMRM) analysis including data up to Week 52/Weeks 49-52 and the following terms: 
 
 Fixed Categorical:	Treatment group, smoking status, geographic region, Visit/Time Period	
 
 Fixed Continuous:	Baseline value	
 
 Repeated:	Visit¹/Time Period	
 
 Interaction Terms:	Visit¹/Time Period by baseline, visit/time period by treatment group.	
 
 
Participants with missing covariate information will be excluded from the analysis
 
1. FEV₁ and FVC recorded at Baseline, Week 24 and Week 52 only.
		Fixed Categorical:	Treatment group, smoking status, geographic region, Visit/Time Period	Fixed Continuous:	Baseline value	Repeated:	Visit ¹ /Time Period	Interaction Terms:	Visit ¹ /Time Period by baseline, visit/time period by treatment group.
Fixed Categorical:	Treatment group, smoking status, geographic region, Visit/Time Period								
Fixed Continuous:	Baseline value								
Repeated:	Visit ¹ /Time Period								
Interaction Terms:	Visit ¹ /Time Period by baseline, visit/time period by treatment group.								

An unstructured covariance structure for the R matrix will be used by specifying 'type=UN' on the REPEATED line. In the event that this model fails to converge, alternative correlation structures may be considered.
									
Model Checking & Diagnostics									

 The Kenward- Roger method for approximating the denominator degrees of freedom and correcting for bias in the estimated variance-covariance of the fixed effects will be used. 									
Model Results Presentation									

 The estimated means for each treatment group will be calculated from the model using the observed marginal distributions of the sample covariates (OM option in LSMEANS statement). Model-estimates of the absolute and change from baseline values will be presented by treatment group. Estimated treatment differences (Mepolizumab-Placebo) with corresponding 95% CIs and p-values will also be presented. 									
Subgroup Analyses									

Separate exploratory subgroup analyses for the change from baseline SGRQ total score will be carried out as outlined in Section 4.10.1.
									

4.4.5. Responders (CAT, SGRQ and E-RS: COPD Responders at Week 24, E-RS: COPD Subscale Responders at Weeks 21-24 and 49-52)

4.4.5.1. Definition of Endpoint

CAT score responders at Week 24: defined as a 2-point or more improvement (reduction) in CAT score from baseline.

SGRQ total score responder at Week 24: defined as a 4-point or more improvement (reduction) in SGRQ total score from baseline.

E-RS: COPD responder at Weeks 21-24: defined as a 2-point or more improvement (reduction) in average E-RS: COPD score from baseline.

E-RS: COPD Breathlessness Sub-Scale responder at Weeks 21-24 and Weeks 49-52: defined as a 1-point or more improvement (reduction) in average E-RS: COPD score from baseline.

E-RS: COPD Cough and Sputum Sub-Scale responder at Weeks 21-24 and Weeks 49-52: defined as a 0.7-point or more improvement (reduction) in average E-RS: COPD score from baseline.

E-RS: COPD Chest Symptoms Sub-Scale responder at Weeks 21-24 and Weeks 49-52: defined as a 0.7-point or more improvement (reduction) in average E-RS: COPD score from baseline.

4.4.5.2. Main Analytical Approach

Approach to analysis will be as described in Section [4.3.2](#).

4.4.6. Patient and Clinician Response to Therapy

4.4.6.1. Patient and clinician-rated response to therapy

Patient-rated and clinician-rated response to therapy are assessed separately. For each, a seven-point scale score is used with the following definitions: 1 = significantly improved; 2 = moderately improved; 3 = mildly improved; 4 = no change; 5 = mildly worse; 6 = moderately worse; and 7 = significantly worse.

Patient-rated and clinician-rated response to therapy will be summarized by visit up to Week 104. Data will be included in the summaries regardless of treatment discontinuation or occurrence of any other intercurrent events.

4.4.6.2. Patient's Global Rating of COPD

The Global Rating of COPD Severity is a single global question that asks participants to rate their severity of COPD on a four-point scale (mild, moderate, severe, very severe). The Global Rating of Change in COPD question is also completed by participants with response options being on a 7-point Likert scale ranging from much better to much worse.

Data will be summarized up to Week 104, and regardless of treatment discontinuation or occurrence of any other intercurrent events.

4.4.7. Healthcare Utilization

The following data will be collected regarding unscheduled use of health care resources:

- Number of Home Visits during Day and Night
- Number of Emergency Room Visits
- Inpatient days in General Ward and Intensive Care
- Number of office/practice visits
- Number of urgent care/outpatient visits

Healthcare utilization associated with an exacerbation will be summarized up to Week 52 only, and regardless of treatment discontinuation or occurrence of any other intercurrent events.

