Overall Design:

This is a multi-center, randomized, placebo-controlled, parallel group, double-blind, trial evaluating mepolizumab 100 mg SC compared with placebo given every 4 weeks as a liquid formulation in a pre-filled safety syringe injection. The study treatment period will be a minimum of 52 weeks up to a maximum of 104 weeks. The study treatment duration for each participant will be determined based on a number of factors, which are detailed in the main body of the study protocol (Section 4.4).

Study inclusion criteria require a blood eosinophil count of ≥ 300 cells/ μ L at Screening Visit 0 and a documented historical blood eosinophil count of ≥ 150 cells/ μ L in the 12 months prior to Screening Visit 0. Historical blood eosinophil count used to meet inclusion criteria must not have been measured within 14 days of a COPD exacerbation. Participants with no documented historical blood eosinophil count of ≥ 150 cells/ μ L must meet this threshold at the Screening Visit 1 assessment. Participants must have a history of regular use of ICS-based triple maintenance COPD therapy (as defined in Inclusion Criteria, Section 5.1) for at least 12 months prior to Screening Visit 1. In addition, for at least 3 months immediately prior to Screening Visit 1, each participant must have a documented history of use of a specific ICS-based inhaled triple maintenance COPD regimen (ICS plus LABA plus LAMA) with a minimum inhaled corticosteroid at a dose of ≥ 500 mcg/day fluticasone propionate or equivalent. Participants are also required to have a history of at least 2 moderate COPD exacerbations that were treated with systemic corticosteroids (intramuscular (IM), intravenous or oral) with or without antibiotics, or 1 severe exacerbation requiring hospitalization in the 12 months prior to Screening Visit 1 and one of the exacerbations has to have occurred while treated with ICS plus LABA plus LAMA. All participants will continue optimized maintenance COPD therapy throughout the entire duration of the study regardless of intervention arm assignment.

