Protocol Activity	Intervention Period and Exit Visit For Weeks 52 to 104 (visit window is ± 7 days)														Early discontinuation /Withdrawal Visit (±7 days)	
	V15 ^a	V16	V17	V18	V19	V20	V21	V22	V23	V24	V25	V26	V27	Exit Visit V28 ^b	Discontinue from IP Visit ^c	Withdraw from study Visit ^c
Study Week	Wk 52 ^a	Wk 56	Wk 60	Wk 64	Wk 68	Wk 72	Wk 76	Wk 80	Wk 84	Wk 88	Wk 92	Wk 96	Wk 100	Wk 104		
Study Day	364	392	420	448	476	504	532	560	588	616	644	672	700	728		
Pre-bronchodilator Spirometry	X						X							X	X	X
Review of eDiary	X	X	X	X	X	X	X	X	X	X	X	X	X	X	X	X
Provide medical problems and healthcare utilization worksheet	X	X	X	X	X	X	X	X	X	X	X	X	X		X	
Review medical problems and healthcare utilization worksheet	X	X	X	X	X	X	X	X	X	X	X	X	X	X	X	X
AE/SAE Assessment	X	X	X	X	X	X	X	X	X	X	X	X	X	X	X	X
Review COPD symptoms summary report (based on eDiary)	X	X	X	X	X	X	X	X	X	X	X	X	X	X	X	X
Administer Interventional Product	X	X	X	X	X	X	X	X	X	X	X	X	X			
eDiary close out														X	X ^h	X
Complete eCRF	X	X	X	X	X	X	X	X	X	X	X	X	X	X	X	X
HRQoL: PRO and Health Outcomes Assessments																
Daily Symptom Diary ⁱ	← X →															
CAT	X						X							X	X	X
SGRQ-C	X						X							X	X	X

Protocol Activity	Intervention Period and Exit Visit For Weeks 52 to 104 (visit window is ± 7 days)														Early discontinuation /Withdrawal Visit (±7 days)	
	V15 ^a	V16	V17	V18	V19	V20	V21	V22	V23	V24	V25	V26	V27	Exit Visit V28 ^b	Discontinue from IP Visit ^c	Withdraw from study Visit ^c
Study Week	Wk 52 ^a	Wk 56	Wk 60	Wk 64	Wk 68	Wk 72	Wk 76	Wk 80	Wk 84	Wk 88	Wk 92	Wk 96	Wk 100	Wk 104		
Study Day	364	392	420	448	476	504	532	560	588	616	644	672	700	728		
EQ-5D-3L	X						X							X	X	X
Clinician rated response to therapy	X			X			X			X				X	X	X
Patient rated response to therapy	X			X			X			X				X	X	X
Patient global rating of COPD severity	X													X	X	X
Patient global rating of change in COPD	X			X			X			X				X	X	X
Home healthcare for study procedures ^j	X	X	X	X	X	X	X	X	X	X	X	X	X			

- a. Procedures listed for V15 at Week 52 only apply to study participants receiving treatment beyond 52 weeks (i.e., Week 52 to a maximum of Week 104). For these participants, a dose of intervention product must be taken at Week 52.

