
Safety Objective
 
 • To evaluate the safety of mepolizumab in participants with COPD 	
 • Incidence of AEs/SAEs including systemic reactions. • Incidence of adjudicated SAE reports and MACE events (CV death, non-fatal myocardial infarction, and non-fatal stroke) • Vital signs including blood pressure (BP), body temperature, pulse rate • ECG assessments • Mortality (all cause including respiratory and cardiovascular causes of death) • Presence of anti-drug antibodies (ADA) to mepolizumab • Hematological and clinical chemistry parameters

Health Outcome Endpoints
 
 • To further evaluate the effect of mepolizumab 100 mg SC on health care utilization. 	
 • Healthcare utilization for COPD including hospitalization, ED, and physician office/clinic visits

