8.10. Health Outcomes Assessments

8.10.1. Medical Resource Utilization and Health Economics

Health Care resource utilization, associated with unscheduled medical encounters, will be recorded by participants in a worksheet and collected in the eCRF by the Investigator and study-site staff for all participants throughout the study. Protocol-mandated procedures, tests, and encounters are excluded.

The data collected about unscheduled use of health care resources may be used to conduct exploratory economic analyses and will include:

- Number and duration of medical care encounters, including surgeries, and other selected procedures (inpatient and outpatient)
- Duration of hospitalization (total days or length of stay, including duration by wards [e.g., intensive care unit, high dependency and usual care])
- Number and type of diagnostic and therapeutic tests and procedures
- Outpatient medical encounters and treatments (including physician or emergency room visits, tests and procedures, and medications).
- Home visits (day and night time)
- Long term oxygen therapy

The resource utilization worksheet used by the participant to record all COPD-related health care contacts experienced since the last visit will be collected and reviewed by the Investigator or designee at the visits indicated in Section 1.3. The Investigator or designated staff should ask the participant if any of the health care contacts that are recorded on the worksheet were due to a COPD exacerbation. The Investigator can refer to his/her records to verify or supplement information given by the participant, if necessary. If any unscheduled healthcare contact is due to a COPD exacerbation, then the Investigator should ensure completion of the COPD Exacerbation section of the eCRF. Details regarding completion of the Healthcare Utilization worksheet are located in the SRM.

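### SAP 4.4.7 summarises only exacerbation-linked healthcare use up to Week 52, so part of the COPD utilization endpoint has no planned summary

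*SAP*

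**What the plan says.** Protocol Section 3 gives the health-outcome endpoint as "Healthcare utilization for COPD including hospitalization, ED, and physician office/clinic visits". The objectives table in SAP 1.1.1 carries the same wording. Neither ties it to exacerbations or to a time point.

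Protocol 8.10.1 says that unscheduled healthcare use is recorded "in a worksheet and collected in the eCRF by the Investigator and study-site staff for all participants throughout the study". The participant's worksheet is "to record all COPD-related health care contacts experienced since the last visit", and the investigator then asks which of those contacts were due to an exacerbation. The schedule for Weeks 52 to 104 (Protocol 1.3.2) continues this: the worksheet is handed out at every visit from Week 52 to Week 100 and reviewed at every visit to Week 104.

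SAP 4.4.7 lists the items (home visits, emergency room visits, inpatient days by ward type, office visits, urgent-care or outpatient visits) and then fixes the summary: "Healthcare utilization associated with an exacerbation will be summarized up to Week 52 only, and regardless of treatment discontinuation".

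**The concern.** SAP 4.4.7 narrows the endpoint in two ways at once: to contacts linked to an exacerbation, and to the first 52 weeks. The SAP therefore disagrees with its own endpoint table, and gives no reason for either limit.

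If the plan is followed literally, two groups of collected data reach no table: COPD contacts that were not part of an exacerbation, and all second-year contact counts and inpatient days. What is at stake is complete reporting of a stated endpoint.

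**Working it through.** The plan gives no figure to reproduce, so the main check is a comparison of the texts.

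**Scope**
- Endpoint (Protocol 3, SAP 1.1.1): healthcare use for COPD.
- Collection (Protocol 8.10.1): all COPD-related contacts, with those due to an exacerbation identified afterwards. Exacerbation-linked contacts are thus a subset by design.
- Summary (SAP 4.4.7): that subset only.

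**Time window**
- Endpoint: no limit stated.
- Collection (Protocol 8.10.1 and 1.3.2): the whole of follow-up, to Week 104 at most.
- Summary (SAP 4.4.7): Week 52.
- General rule for efficacy data (SAP 4.1.1): up to Week 104 where available. The neighbouring descriptive outputs (response to therapy, global ratings and EQ-5D-3L, in SAP 4.4.6 and 4.4.7.1) all run to Week 104.

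**Is the remainder picked up elsewhere?** In part. The ED/hospitalisation rate in SAP 4.3.5, the time-to-first analyses in 4.4.1 and the severe exacerbation rate in 4.4.2 use follow-up to Week 104. They count exacerbations. No other section tabulates home, office, urgent-care or emergency visits, or inpatient days.

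**Size of the time restriction.** Protocol 1.1 says: "The study treatment period will be a minimum of 52 weeks up to a maximum of 104 weeks". Let f be the fraction of participants extended beyond Week 52 and m their mean extra weeks. Neither is in the documents, so both are assumptions. With N participants, planned follow-up is N(52 + f·m) weeks, of which N·f·m falls after Week 52. The share dropped is

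f·m / (52 + f·m)

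| f | m (weeks) | f·m | Share of planned follow-up dropped |
|---|---|---|---|
| 0.25 | 26 | 6.5 | 6.5/58.5 = 11% |
| 0.50 | 26 | 13 | 13/65 = 20% |
| 0.50 | 52 | 26 | 26/78 = 33% |
| 0.75 | 52 | 39 | 39/91 = 43% |
| 1.00 | 52 | 52 | 52/104 = 50% |

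The last row is a ceiling that cannot quite be reached, because the last randomised participant is scheduled for 52 weeks only. For 800 participants, the first row is 800 × 0.25 × 26/52 = 100 participant-years, and the last is 800.

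These are shares of planned follow-up, ignoring early withdrawal. They are shares of contacts only if the contact rate is constant over time. The exacerbation-only restriction cannot be sized, because the documents do not say what proportion of COPD contacts falls outside exacerbations.

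**The case against.** The other side has several fair points.

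- **Delegation.** Protocol 9.4.3.1 leaves the summary of health-outcome data to the analysis plan, and Protocol 8.10.1 speaks only of possible exploratory economic use. This stands. It means that the absence of an entry in the SAP 4.12 table of changes is weak evidence of an undeclared protocol change, and the point does not rest on it. Delegation does not explain why SAP 4.4.7 is narrower than the endpoint in SAP 1.1.1.
- **A common window.** Every participant is expected to complete 52 weeks, later follow-up varies, and the SAP uses Week 52 for other outputs, such as the diary and change-from-baseline models. A Week 52 table of raw counts is defensible and should stay. This argument does not cover the exacerbation-only restriction.
- **Low stakes.** The endpoint is descriptive and sits outside the testing hierarchy. This stands and sets the severity.

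A reader might also infer more than the documents support:

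- *That second-year ED and hospital care goes wholly unreported.* It does not. SAP 4.3.5 defines its endpoint as "Frequency of exacerbations requiring ED visit and/or hospitalization over the study treatment period (up to 104 weeks" at most), and SAP 4.4.1 and 4.4.2 also use those events.
- *That the utilization table should agree with step 6 of the hierarchy.* Nothing requires it. One output counts visits and days whatever intercurrent events occur. The other counts exacerbations, merges those within 7 days of each other, and sets data after COVID-linked treatment discontinuation or interruption to missing (SAP 4.2.1). A longer window would not make them match.
- *That the planned table ignores person-time, or that interval precision is lost.* SAP 4.4.7 specifies no display format and no confidence intervals, so neither criticism has a planned output to attach to.

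**Conclusion.** The inconsistency is real and minor. SAP 4.4.7 does not deliver the endpoint stated in Protocol 3 and SAP 1.1.1. COPD contacts unrelated to an exacerbation, and second-year contact-level counts and inpatient days, are collected with no planned summary. Type I error, power, the primary result and the ranked secondary endpoints are unaffected.

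The Week 52 limit removes between 11% and, at the ceiling, 50% of planned follow-up over the scenarios shown, all of which rest on assumed values of f and m. A smaller extension would give a smaller share. The conclusion also takes the protocol at its word that all COPD-related contacts reach the eCRF, which is not among the documents.

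**What to change.** In SAP 4.4.7, summarise all COPD-related unscheduled contacts to the end of each participant's analysis period (up to Week 104), by arm, as counts and as rates per participant-year. Use actual time in study as the denominator, taking the combined on- and off-treatment length in SAP 6.2.2.2, since 4.4.7 keeps data after intercurrent events. Show exacerbation-associated contacts as a subset, and retain the Week 52 table as the common-window display.

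The cost is a wording change and one or two further descriptive tables, with no new data collection. The drawback is unequal follow-up in the full-period table, which the per-participant-year rate addresses.
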